		Appendix adenoma	
		Benign anorectal neoplasm	
		Colon adenoma	
		Large intestine fibroma	
		Large intestine polyp	
		Rectal adenoma	
		Rectal polyp	
		Benign duodenal neoplasm	
		Benign gastric neoplasm	
		Benign oesophageal neoplasm	
		Duodenal polyp	
		Gastric adenoma	
		Gastric cyst	
		Gastric leiomyoma	
		Gastric polyps	
		Oesophageal cyst	
		Oesophageal papilloma	
		Oesophageal polyp	
		Biliary cyst	
		Biliary polyp	
		Choledochal cyst	
		Congenital cystic disease of liver	
		Gallbladder polyp	
		Haemorrhagic hepatic cyst	
		Hepatic cyst	

Document: T:\PROJ\Shire\UYA25606\_Biostatistics\Documentation\SAP\SAP\SHP633-306\_SAP\_Final  
v2.0\_20180415.docx

Author: [REDACTED] Version Number: Final V2.0  
Version Date: 15Apr2019

Groupings	System Organ Class (SOC)	Preferred Terms (PT)	Higher Level Group Terms (HLGTs)
		Hepatic cyst infection	
		Hepatic cyst ruptured	
		Hepatobiliary cyst	
		Benign biliary neoplasm	
		Benign hepatic neoplasm	
		Benign hepatobiliary neoplasm	
		Benign neoplasm of ampulla of Vater	
		Biliary adenoma	
		Biliary hamartoma	
		Cholangioadenoma	
		Focal nodular hyperplasia	
		Gallbladder adenoma	
		Gallbladder papilloma	
		Haemangioma of liver	
		Hepatic adenoma	
		Hepatic haemangioma rupture	
		Hepatic hamartoma	

Note: MedDRA terms are based on MedDRA version 21.0.

Document: T:\PROJ\Shire\UYA25606\_Biostatistics\Documentation\SAP\SAP\SHP633-306\_SAP\_Final  
v2.0\_20180415.docx

Author: [REDACTED] Version Number: Final V2.0  
Version Date: 15Apr2019

Template No: Harmonized Statistical Analysis Plan Template v1.0

Effective Date: 01June2018

## 2 LIST OF ABBREVIATIONS

Term	Definition
AUC 0-t	Area under the plasma concentration-time curve from time zero to the last measurable concentrations, calculated using the linear trapezoid rule.
AUC 0-inf	Area under the plasma concentration time curve from time zero to infinity
BLQ	Below limit of quantification
CL/F	Apparent clearance
C max	Maximum plasma concentration
CSC	Certara Strategic Consulting
CV%	Coefficient of variation
eCRF	Electronic case report form
EDT	Electronic Data Transmission
GLP-2	Glucagon-like peptide-2
LLOQ	Lower limit of quantitation
$\lambda_z$	Lambda z, first-order rate constant of the terminal elimination phase
Max	Maximum
Mean	Arithmetic mean
Min	Minimum
N	Sample size
NCA	Non-compartmental analysis
PK	Pharmacokinetics(s)
PN/IV	Parenteral nutrition or intravenous
QD	Once daily
SBS	Short bowel syndrome
SC	Subcutaneous
SD	Standard deviation
FTP	Secure File Transfer Protocol
SOP	Standard operating procedures
$t_{1/2}$	Terminal elimination half-life
T last	Time of time of the last quantifiable concentration
T max	Time of maximum observed plasma concentration
Vz/F	Apparent volume of distribution

### 3 BACKGROUND

This pharmacokinetic (PK) Analysis Plan was created using the study protocol SHP633-306 (Amendment 1, dated 27 Sep 2018). Any further changes to the protocol may require updates to the current analysis plan.

Teduglutide is a novel, recombinant analog of naturally occurring human glucagon-like peptide-2 (GLP-2) that regulates the functional and structural integrity of the cells lining the gastrointestinal tract. Teduglutide is a 33-amino acid peptide that differs from native GLP-2 in the substitution of glycine for alanine at the second position at the N-terminus. As a result, teduglutide demonstrates resistance to degradation by dipeptidyl peptidase 4 and therefore maintains a longer elimination half-life ( $t_{1/2}$ ) of approximately 2 hours compared to the native peptide, which has a  $t_{1/2}$  of approximately 7 minutes. Teduglutide has been shown in animal studies and previous human clinical trials to increase villus height and crypt depth in the intestinal epithelium, thereby increasing the absorptive surface area of the intestines.

This analysis plan addresses the PK of teduglutide (0.05 mg/kg) following subcutaneous (SC) administration in Japanese subjects with short bowel syndrome (SBS) who are dependent on parenteral nutrition or intravenous (PN/IV) support. The intended methods of data analysis and reporting are included in the current analysis plan. This document provides guidance to the extent, scope, and method of analysis. However, due to uncertainty of the nature of the data a priori, deviations from this plan may be necessary and will be documented.

### 4 ANALYSIS PLAN OBJECTIVES

The specific objective of this project is to summarize the PK of teduglutide after a SC administration of teduglutide 0.05 mg/kg in adult Japanese subjects with SBS who are dependent on PN/IV support. PK parameters will be derived using non-compartmental analysis (NCA).

### 5 STUDY DESIGN

[figure not shown]
Protocol SHP633-306 was an open-label, multicenter study, consisting of a conditional PN/IV optimization period, a mandatory PN/IV stabilization period, and a 24-week treatment period.

Japanese male or female subjects 16 years of age or older (at the time of signing informed consent) were considered eligible for the study. If at screening, a subject did not have an optimized PN/IV volume, defined as a 48-hour urine output between 2 and 4 L, he/she entered the optimization period, during which the minimally tolerated stable PN/IV volume was determined during a period of up to 8 weeks. If it was not possible to keep the subject adequately hydrated and nourished within the target urine output range, the minimally tolerated PN/IV volume was documented.

All subjects entered the stabilization period, during which the target PN/IV volume was maintained for at least 4 consecutive weeks (8 weeks maximum). Following the stabilization period, subjects entered a 24-week dosing period, during which all subjects received teduglutide 0.05 mg/kg SC once daily. At each site visit during the treatment phase, efficacy (adjustments to PN/IV) and safety was monitored.

A schematic representation of the study design is presented in [Figure 1](#).

**Figure 1. Study Design (SHP633-302)**

Teduglutide (0.05 mg/kg) was administered SC once daily into 1 of the 4 quadrants of the abdomen or either thigh or arm for 24 weeks. Subjects had blood samples taken for teduglutide PK analysis at predose, at 15, 30 minutes and 1, 2, 3, 4, 6, 8, 10, and 12 hours post dose at Visit 2. Subjects also had blood samples taken for teduglutide PK analysis at predose and 1 and 2 hours post dose at Visit 5 (Week 4) or Visit 7 (Week 12) of the treatment period. The first dose of teduglutide was administered by the study physician at the baseline visit (Visit 2). At this visit, subjects had blood samples taken for teduglutide PK analysis:

- 0-hour (predose) draw: any time prior to the dose
- 15 minutes postdose:  $\pm 5$  minutes
- 30 minutes postdose:  $\pm 5$  minutes
- 1 hour postdose:  $\pm 10$  minutes
- 2 hours postdose:  $\pm 10$  minutes
- 3 hours postdose:  $\pm 10$  minutes
- 4 hours postdose:  $\pm 30$  minutes
- 6 hours postdose:  $\pm 30$  minutes
- 8 hours postdose:  $\pm 30$  minutes
- 10 hours postdose:  $\pm 30$  minutes
- 12 hours postdose:  $\pm 30$  minutes

Subjects also had blood samples taken for teduglutide PK analysis at Week 4 (Visit 5) or Week 12 (Visit 7):

- 0-hour (predose) draw: any time prior to the daily dose, on the day of dosing, but at least 14 hours after the previous dose
- 1 hour postdose:  $\pm 10$  minutes
- 2 hours postdose:  $\pm 10$  minutes

All subjects who completed the study may have participated in a long-term extension study (SHP633-307) in which they continued receiving teduglutide.

## 6 ANALYSIS SET

The PK population will consist of all enrolled subjects who received at least one SC injection of teduglutide and have evaluable and interpretable PK profile.

## 7.2 Noncompartmental PK Analysis

### 7.2.1 Concentration Data

Observed concentration values of plasma teduglutide that are reported as below the limit of quantitation (BLQ) will be set to zero for PK analysis and summary statistics.

### 7.2.2 Pharmacokinetic Parameters of Teduglutide

All plasma PK parameters will be derived using actual or nominal times (when actual time is not available) relative to the time of study drug administration. PK parameters will be derived using NCA methods based on individual plasma concentration-time data for teduglutide collected at baseline (day 0) (or at any other future site visit if subject was unable to provide blood samples at day 0) as described in [Table 1](#).

**Table 1. PK Parameters Teduglutide in Plasma**

Parameters	Definitions
AUC 0-t	Area under the plasma concentration-time curve from time zero to the last measurable concentrations, calculated using the linear trapezoid rule.
AUC 0-inf	Area under the plasma concentration time curve from time zero to infinity, calculated using the formula AUC 0-t + (C last / λ Z ), where C last is the last quantifiable concentration. The AUC 0-inf will be calculated using the linear trapezoid rule. If the percent of extrapolation (% AUC Extrap ) is > 20%, the value of AUC 0-inf (and other derived parameters such as CL/F and V Z /F) will be reported but not taken into account in the calculation of descriptive statistics.
λ Z	First-order rate constant of the terminal elimination phase, calculated by log-linear regression analysis over the terminal log-linear segment of the plasma concentration-time curve. Assessments of λ Z included the key considerations listed below this table.
t 1/2	Terminal elimination half-life, calculated as ln(2) / λ Z . Assessments of t 1/2 followed the key considerations for λ Z , as listed below this table.
% AUC Extrap	The percentage of AUC 0-inf estimated by extrapolation from T last to infinity, calculated as (AUC 0-inf – AUC 0-t ) / AUC 0-inf x 100.
CL/F	Apparent clearance, calculated as Dose / AUC 0-inf .
V Z /F	Apparent volume of distribution, calculated as Dose / AUC 0-inf x λ Z .

The assessments of λZ will include the following considerations:

- At least 3 time points (in which the first time point must be greater than tmax) with measurable serum concentrations were required for the calculation of λZ.
- λZ must be positive, and calculated from at least three data points in the terminal phase of the concentration-time profile.
- Points prior to Cmax are not used.
- R^2 adj ≥ 0.7 for the log-linear regression analysis of λZ.

No value for λZ and related parameters (eg, AUC0-inf, t1/2, CL/F and/or VZ/F) will be reported for concentration-time profiles that do not exhibit an elimination phase in the concentration versus time profile (ie, if R^2 adj < 0.7 for the log-linear regression analysis of λZ).

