1.2 Product Background and Clinical Information

Teduglutide is a novel, recombinant analog of naturally occurring human GLP-2 that regulates the functional and structural integrity of the cells lining the gastrointestinal (GI) tract.

Teduglutide is a 33-amino acid peptide that differs from native GLP-2 in the substitution of glycine for alanine at the second position at the N terminus. As a result, teduglutide demonstrates resistance to degradation by dipeptidyl peptidase 4 and therefore maintains a longer elimination half-life of approximately 2 hours in healthy subjects and 1.3 hours in adult SBS subjects compared to the native peptide, which has a $t_{1/2}$ of approximately 7 minutes. Teduglutide has been shown in animal studies and previous human clinical trials to increase villus height and crypt depth in the intestinal epithelium, thereby increasing the absorptive surface area of the intestines.

Results of the pivotal study, CL0600-020, showed that teduglutide at a dose of 0.05 mg/kg/day for up to 24 weeks was superior to placebo in reducing PN/IV support in adult subjects with SBS. In this study the responder rate (defined as at least a 20% reduction from baseline in weekly PN/IV volume at Week 20 and Week 24) was 62.8% in the teduglutide 0.05 mg/kg/day group with subjects achieving a mean reduction from baseline in PN/IV volume of 4.4 L/week at Week 24.

In the follow-up long-term extension study CL0600-021, there continued to be evidence of increased efficacy of teduglutide over time in all groups exposed to teduglutide in terms of PN/IV volume reduction, gaining additional days off per week, and achieving complete weaning of PN/IV. The most significant reductions were for those subjects who received 24 weeks of teduglutide 0.05 mg/kg/day in CL0600-020 and continued treatment in CL0600-021 for another 24 months. In this cohort, 10 subjects completely weaned off of PN/IV support and 18/30 (60.0%) had a reduction in their PN/IV requirement of at least 3 days per week. It was encouraging that efficacy was also observed for subjects who initiated treatment in CL0600-021 (ie, those who received placebo or were not treated in CL0600-020).

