## 7.5 Software

Dataset set construction, tables and figures will be generated using Phoenix NLME (Version 7.2 or higher), Phoenix™ WinNonlin® (6.3 or later), R® (Version 3.3.1 or higher) or SAS.

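### The PK plan's formula for Vz/F lacks brackets: evaluated as written it multiplies CL/F by λz instead of dividing by it

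*SAP*

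**What the plan says.** The protocol (section 9.9) lists V/F among six PK parameters to be derived and gives no formula. The main SAP (section 8.1) leaves the derivation to a vendor working to the separate PK analysis plan, so Table 1 in section 7.2.2 of that plan is the operative definition. The relevant rows are:

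- CL/F: "Apparent clearance, calculated as Dose / AUC"0-inf.
- Vz/F: "Apparent volume of distribution, calculated as Dose / AUC"0-inf × λz. No brackets group the AUC with λz.
- λz: "First-order rate constant of the terminal elimination phase", with t1/2 = ln(2)/λz, so its unit is 1/h.
- % AUC extrapolated: (AUC0-inf − AUC0-t) / AUC0-inf × 100.

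The shell for Table 14.3.1 in Appendix 2 of the PK plan reports CL/F in L/h and Vz/F in L. Neither the protocol nor the SAP states another Vz/F formula.

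**The concern.** Under ordinary precedence, division and multiplication rank equally and are taken left to right. The Vz/F row then means (Dose / AUC0-inf) × λz. Apparent volume requires λz in the denominator, so the stated expression is not a volume and cannot carry the unit in the shell.

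PK is one of the study's stated objectives, and the written formula is the natural reference for the programmer and for the quality-control reviewer. If both followed it exactly, Vz/F would be wrong for every subject whose λz differs from 1/h. The error factor depends on each subject's own λz, so no single constant would repair the summary table afterwards. The geometric mean and CV% would be distorted as well.

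**Working it through.** The plan states no numerical value for Vz/F, so there is no figure to reproduce. The check covers units, the table's own notation, and the size of the discrepancy.

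**Inputs**
- The formulas for CL/F, Vz/F, λz and % AUC extrapolated: PK plan, Table 1.
- Reporting units: PK plan, Appendix 2, shell for Table 14.3.1.
- Half-lives: protocol section 1.2, "approximately 2 hours in healthy subjects and 1.3 hours in adult SBS subjects"; PK plan section 3, "of approximately 2 hours compared to the native peptide".

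**1. Units**
- As written: (Dose / AUC0-inf) × λz = CL/F × λz, in (L/h) × (1/h) = L/h².
- With brackets: Dose / (AUC0-inf × λz) = (CL/F) / λz, in (L/h) / (1/h) = L.

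Only the bracketed form matches the shell.

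**2. Which reading the table itself uses**

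The % AUC extrapolated row has the same pattern, A / B × C. Take illustrative values AUC0-inf = 200 and AUC0-t = 180:
- left to right: (200 − 180) / 200 × 100 = 10%, which is correct;
- denominator grouped: (200 − 180) / (200 × 100) = 0.001, which is not the percentage.

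That row works only left to right. The Vz/F row works only with the denominator grouped. One convention cannot serve both.

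**3. Size**

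Ratio of literal to correct value = (CL/F × λz) / ((CL/F) / λz) = λz². Dose, body weight and AUC cancel.

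| t1/2 | λz = ln(2)/t1/2 | λz² | Understatement, 1/λz² |
|---|---|---|---|
| 1.3 h | 0.533/h | 0.284 | 3.5-fold |
| 2 h | 0.347/h | 0.120 | 8.3-fold |

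The two forms agree numerically only when λz = 1/h, that is at t1/2 = ln(2) = 0.69 h.

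**4. Illustration**

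Body weight and AUC here are assumptions, not figures from the documents: 50 kg, so 0.05 × 50 = 2.5 mg, and AUC0-inf = 200 ng·h/mL. Then CL/F = 2,500,000 ng / 200 ng·h/mL = 12,500 mL/h = 12.5 L/h.

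| t1/2 | Literal: 12.5 × λz | Correct: 12.5 / λz |
|---|---|---|
| 1.3 h | 6.67 L/h² | 23.4 L |
| 2 h | 4.33 L/h² | 36.1 L |

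At fixed CL/F the literal result falls as half-life lengthens, while the true volume rises. Over assumed weights of 40 to 60 kg and AUC0-inf of 100 to 400 ng·h/mL, the ratios stay at 0.284 and 0.120.

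**The case against.** The strongest reply is that this is a slip of notation whose meaning is recoverable. The shell asks for L, CL/F is in L/h and λz is a rate constant, so only one formula fits, and a PK analyst would recognise it. Section 7.2.2 calls for non-compartmental methods with a textbook reference. Section 7.5 lists Phoenix WinNonlin, and a standard package would normally compute Vz/F without reference to this line. Section 7.6 requires two-person quality control, and a wrong Vz/F would sit beside the CL/F and t1/2 that expose it. The parameter is only summarised descriptively, in a study planned for at least 5 subjects, and no decision rule in the documents uses it.

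Most of that stands, and it limits both the likelihood and the consequence of an error. Two points remain:

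- The software section does not settle which tool derives the parameter. It says "Dataset set construction, tables and figures will be generated using Phoenix NLME" and then also lists WinNonlin, R and SAS. Because it speaks of datasets, tables and figures, it neither shows that Vz/F will be hand-coded nor commits it to a packaged routine.
- Quality control against the plan checks against the faulty line.

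Loss of brackets in reading the PDF is an unlikely explanation, because brackets survive in neighbouring rows and the slash is printed inline.

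On size, 1.3 h is the protocol's figure for the population studied. The 2 h figure is the protocol's for healthy subjects, and the PK plan repeats it without naming a population. The 0.28 ratio is therefore the more relevant of the two.

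**Conclusion.** The concern holds. As written, the formula yields CL/F × λz in L/h², which contradicts the plan's own reporting unit. Followed exactly, it would understate Vz/F about 3.5-fold at a half-life of 1.3 h and about 8.3-fold at 2 h. Those factors rest on the half-lives quoted in the documents and apply only if the line is programmed literally; the documents do not show that it was. AUC, Cmax, tmax, t1/2 and CL/F are unaffected. This is a minor correction to the specification and does not threaten the study's conclusions.

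**What to change.** In PK plan Table 1, write Vz/F = Dose / (AUC0-inf × λz), or equivalently (CL/F) / λz. Confirm that any program or quality-control check that computes Vz/F uses this form; recomputing it as (CL/F) × t1/2 / ln(2) from the listed parameters is enough. The cost is one pair of brackets and a short check. No design, data collection or analysis choice changes.

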## 7.3 Statistical Methods

### 7.3.1 Concentrations of Teduglutide

Individual teduglutide concentrations will be listed and summarized in accordance with the grouping factors (ie, by treatment and for single dose and multiple doses, if applicable). Each data subset will be listed by subject and summarized for each nominal time point. If the actual time of blood collection post dose deviates by >20% from the nominal time, those sample concentrations will be reported and included in the PK analysis but excluded from summary statistics of concentration tables and mean figures.

Concentration data will be summarized at each nominal time point with the following descriptive statistics: sample size (n), arithmetic mean (Mean), standard deviation (SD), coefficient of variation (CV%), median (Median), minimum (Min), maximum (Max).

Individual concentrations of teduglutide will be reported at the level of significance presented in the observed data files. Reporting rules for the concentrations and summary statistics, will be as follows:

- Mean: 1 more level of significance than the individual value
- SD: 1 more level of significance than the mean
- CV%: always 1 decimal
- Median, Min, Max: at the level of significance reported for the individual value.

Mean concentrations will be reported as zero if all values are zero, and no descriptive statistics will be reported. If the calculated mean concentration is less than the lower limit of quantitation (LLOQ = 1 ng/mL), the value will be reported as calculated. A minimum of three values will be required for calculation of descriptive statistics.

Mean (+SD) teduglutide concentrations vs. nominal sampling time will be presented on linear-linear and log-linear scales by treatment for single dose (day 0) and multiple doses (ie, unscheduled visit, if applicable).

### 7.3.2 PK Parameters of Teduglutide

Individual plasma teduglutide PK parameters will be listed and summarized in accordance with the grouping factors (ie, by treatment and for single dose and multiple doses, if applicable) with the following descriptive statistics: n, Mean, SD, CV%, Median, Min, Max, Geometric Mean and CV% Geometric Mean.

Reporting rules for the PK (with the exception of  $C_{max}$ ) and summary statistics will be as follows:

- Individual values with the number of decimals that will allow 3 significant figures to be presented for the minimum value of the parameter, except for  $t_{max}$  which are parameters of time to be reported with 2 decimals.
- Mean and Geometric Mean: 1 more decimal than the individual value

- SD: 1 more decimal than the mean
- CV% and CV% Geometric Mean: always 1 decimal
- Median, Min, Max: same number of decimals as the individual value

Individual and summary statistics for the PK parameter  $C_{\max}$  will follow the reporting rules described for teduglutide concentrations (Section 7.3.1).

Mean concentrations will be reported as zero if all values are zero, and no descriptive statistics will be reported. A minimum of three values will be required for calculation of descriptive statistics.

## 7.4 Data Handling

### 7.4.1 Handling of Missing Plasma Concentrations

PK parameters will be calculated for subjects with sufficient plasma sample data to assess PK parameters, ie with at least 2 postdose concentrations. Concentrations for subjects with missing samples will not be excluded from the concentration summary statistics.

For the PK parameter calculations following a single dose (Day 0), a missing predose value will be set to zero. For the PK parameter calculations following multiple doses (ie, any other future site visit after day 0), a missing predose value will be set to the median value observed in the treatment group, if available.

Unless otherwise noted, data summaries will be performed only on observed data.

### 7.4.2 Handling of Incomplete and/or Non-Compliant Data

Subjects with incomplete dosing information or plasma concentration-time profiles will be reviewed by CSC and Takeda for inclusion/exclusion into the PK Population. Missing dose or sampling dates and/or times may be imputed using nominal times. The imputation strategy will be discussed with Takeda. All samples associated to a missing dosing date and/or time that cannot be imputed will be excluded from the analysis.

### 7.4.3 Unexpected Data

After database lock, a visual inspection of concentration-time profiles will be performed to determine dataset integrity and potential outliers. Subjects with potential outlier data will be reviewed by CSC and Takeda for inclusion/exclusion from the descriptive statistics on a case-by-case basis.

Any plasma concentrations that cannot be uniquely and unequivocally attributed to a particular subject, visit, or time point based on eCRF records or other observed data records in the study will be treated as incomplete data. Such data will be compiled, commented, and listed separately in the appendix of the report. Incomplete and/or non-compliant data, if any, will be excluded from analysis datasets; no analyses, summaries or graphs will be produced using these data.

Multiple observations at the same time point will be averaged for the calculation of PK parameters.

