4 STUDY POPULATION

At least 5 Japanese subjects with PN/IV-dependent SBS will be dosed.

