4.4 Discontinuation of Subjects

A subject may withdraw from the study at any time for any reason without prejudice to their future medical care by the physician or at the institution. The investigator or sponsor may withdraw the subject at any time (eg, in the interest of subject safety). The investigator should discuss withdrawal of a subject from investigational product with the medical monitor as soon as possible.

If investigational product is discontinued, regardless of the reason, the evaluations listed for Visit 10 are to be performed as completely as possible. Whenever possible, all discontinued subjects should also receive a follow-up phone call 4 weeks after the last dose of study drug unless the subject has withdrawn consent. Comments (spontaneous or elicited) or complaints pertaining to study drug discontinuation made by the subject must be recorded in the source documents. The reason for termination, date of stopping investigational product, and the total amount of investigational product taken must be recorded in the electronic case report form (eCRF) and source documents.

Subjects who discontinue will not be replaced.

Subjects who do not enroll in the treatment extension study or who discontinue prematurely at any time during the study will receive a follow-up phone call 4 weeks after the last dose of study drug.

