9.5 Sample Size Calculation and Power Considerations

The sample size of the SHP633-306 study is based on patient prevalence and study design elements; no statistical estimation was involved. Possible medical institutes for SBS studies are limited, given the rarity of the disease and the very limited number of patients with SBS (<1000) in Japan. The applicant considers that 5 treated subjects in SHP633-306 should provide sufficient basic information concerning the efficacy, safety and tolerability as well as PK of teduglutide in the Japanese study population.

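### PK SAP 7.4.3 lets suspected outliers be dropped from the PK summaries after lock without a documented cause, which with about five subjects can shift the mean and usually understates variability

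*SAP*

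**What the plan says.** The rule is in the first paragraph of PK SAP 7.4.3: "After database lock, a visual inspection of concentration-time profiles will be performed to determine dataset integrity and potential outliers". It continues: "Subjects with potential outlier data will be reviewed by CSC and Takeda", with the outcome being "inclusion/exclusion from the descriptive statistics on a case-by-case basis". The unit is the subject, the trigger is appearance, and the decision is joint. The section sets no numerical limit, does not ask for an identified error, and does not say that the reason or an all-subjects result must be reported.

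Other data problems have their own rules in the same plan:

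- Section 7.4.2 covers incomplete dosing information and incomplete profiles.
- The second paragraph of 7.4.3 covers samples that cannot be attributed to a subject, visit or time.
- Section 7.2.2 sets limits for AUC extrapolation (above 20%) and adjusted R² (below 0.7).
- Section 7.3.1 sets a limit for sampling-time deviation (above 20%).

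The outlier clause is therefore a separate discretion, additional to these rules.

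Parameters are summarised under PK SAP 7.3.2 "with the following descriptive statistics: n, Mean, SD, CV%, Median, Min, Max, Geometric Mean and CV% Geometric Mean", provided at least three values are available. On numbers, Protocol section 4 says: "At least 5 Japanese subjects with PN/IV-dependent SBS will be dosed". Protocol 9.5 adds that "no statistical estimation was involved", and Protocol 4.4 that "Subjects who discontinue will not be replaced".

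**The concern.** PK in Japanese subjects is one of the study's stated objectives, and no PK hypothesis is tested, so the descriptive statistics are the PK result. If people who have seen the values can remove a subject because the profile looks unusual, the reported mean, SD and CV% describe a selected subset. With five subjects each carries a fifth of the weight. Because three values are enough for a summary, two of five could be removed and the table would still be produced.

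The gap is not closed elsewhere. Protocol 9.3 promises that the SAP will describe the handling of spurious data, and main SAP 11.5 carries that title, but it contains no outlier rule. PK SAP section 3 says deviations from the plan will be documented. An exclusion made under 7.4.3 follows the plan, so that sentence does not reach it.

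**Working it through.** **Inputs.** n = 5 is the planned minimum (Protocol 4 and 9.5). The plan has no calculation to reproduce, because the sample size was set by prevalence and feasibility. Between-subject CV is not in the documents, so it is assumed and shown as a range.

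**Step 1: algebra for one removed subject.** Let the removed value lie k sample SDs above the mean of n values.

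- Fall in the mean = k/(n − 1) SD.
- New SD = old SD × √{[(n − 1) − n·k²/(n − 1)]/(n − 2)}.
- Largest possible k = (n − 1)/√n = 4/√5 = 1.789 at n = 5.

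At n = 5 and k = 1.5:

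- The mean falls by 1.5/4 = 0.375 SD. That is 11.2% of the mean at an observed CV of 30% and 15.0% at 40%.
- The SD is multiplied by √[(4 − 1.25 × 2.25)/3] = 0.629.

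**Step 2: invented example.** Take 80, 90, 100, 110, 220.

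- The mean is 120.0. The SD is √(13,000/4) = 57.0. The CV is 47.5% and the geometric mean 111.7.
- Without 220, the mean is 95.0, the SD 12.9, the CV 13.6% and the geometric mean 94.3.

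**Step 3: lognormal samples with no true outlier.** There were 200,000 samples of n = 5 at each assumed CV. Two selection habits were compared.

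| True CV | Highest dropped: average change in mean | Most extreme on log scale dropped: average change in mean |
|---|---|---|
| 30% | −9.2% | −1.3% |
| 40% | −12.4% | −2.2% |
| 50% | −15.4% | −3.3% |

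*Observed CV, highest dropped.* After/before ratios are 0.78, 0.77 and 0.77 at true CV 30%, 40% and 50%. At 40% the average observed CV goes from 35.7% to 27.6%.

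*Observed CV, most extreme on the log scale dropped (medians).*

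- True CV 30%: 26.5% to 17.0%, a fall of 1 − 17.0/26.5 = 36%.
- True CV 40%: 34.4% to 22.3%, a fall of 35%.
- True CV 60%: 48.4% to 31.7%, a fall of 35%.

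The average change in the mean is small under the second habit because falls and rises largely cancel over repetitions. In any one study the move is larger: the median absolute change is 9.3% at CV 30% and 11.9% at CV 40%, in either direction.

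**Step 4: how often variability falls.** When the highest value is dropped, the CV still rises in 18%, 20% and 22% of samples at true CV 30%, 40% and 50%. When the value most extreme on the log scale is dropped, the SD falls in at least 99.9% of samples.

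**Step 5: more subjects.** At n = 11 and CV 40%, dropping the highest changes the mean by a median −6.9%, against −11.3% at n = 5. The median CV goes from 36.9% to 31.2%, a fall of 15%, against 34.4% to 26.7%, a fall of 22%, at n = 5.

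**The case against.** The strongest case against is that little is hidden. Individual concentrations and parameters are listed, individual profiles are plotted, and the shell for Table 14.3.1 sets each subject's row above a summary that includes N and the median. With about five rows, a reader can see that someone is missing and recompute. Main SAP 8.2 also summarises concentrations on the PK Population, with no outlier exclusion stated. Visual inspection only flags candidates, and a joint review decides. The study is descriptive, so no error rate is affected. The vendor procedures cited in PK SAP 7.6 are not available here and might address outliers.

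Most of this stands, and it limits the point. It does not remove it: the parameter summaries are produced only under the PK SAP, and readers quote the summary lines.

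A reader might infer three stronger things that the documents do not support:

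- **That exclusion always understates variability.** It does not; the CV rises in about a fifth of samples when the highest value is dropped.
- **That a 9–15% fall in the mean is the general consequence.** Those figures belong to always dropping the highest value. Section 7.4.3 does not say that high values are the ones removed, or that any flagged subject must be.
- **That unblinded review is the problem.** In a single-arm, open-label study there is no allocation to reveal and no comparison to steer.

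**Conclusion.** The point holds in a limited form. PK SAP 7.4.3 allows removal of subjects after lock, on appearance, with no required cause and no with-and-without summary. With a planned minimum of 5, this can shift the reported PK-parameter mean and will usually, not always, make between-subject variability look smaller.

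The size depends on which value is dropped. It is a 9–15% average fall in the mean and about a fifth off the CV for the highest value, or a 1–3% average fall and about a third off the CV for the most extreme value on the log scale. These figures assume lognormal exposure, a CV of 30–50%, exactly 5 subjects and one genuine value removed every time, so they illustrate the rule's reach rather than forecast its effect. More subjects would shrink them.

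The exposure lies mainly in the PK-parameter summaries, and also in the PK SAP's own concentration tables and mean figures. Nothing in the documents shows that any subject was excluded this way.

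**What to change.** Change only the outlier clause of PK SAP 7.4.3. Keep suspected outliers in the main summary unless a dosing, sampling or assay error is documented. Show any summary without a suspected outlier as a labelled second table that names the subject number and the reason.

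Leave the prespecified rules on extrapolation and adjusted R² (7.2.2) and on sampling-time deviation (7.3.1) as they are. A blanket instruction to include every subject with data would contradict them.

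The cost is one paragraph and at most one extra table, with no new data. Reported variability may be larger.
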